5.4 APPROPRIATENESS OF MEASUREMENTS

The efficacy tests, instruments and scales used in this trial are widely used and considered reliable, accurate, and relevant in trials for the indication of pain relief.

c03317678-02 Trial Protocol Page 44 of 69

Proprietary confidential information © 2016 Boehringer Ingelheim International GmbH or one or more of its affiliated companies

6. INVESTIGATIONAL PLAN

6.1 VISIT SCHEDULE

This trial consists of 6 clinical visits. For the follow-up contact (Visit 7T) the investigator will contact the patient by phone.

If a Visit 2-5 is missed, it should not be re-scheduled. However subsequent visits should follow the original visit schedule. If Visit 6 or Visit 7T is missed, this visit should be rescheduled to the closest opportunity.

All trial visits except for Visit 3 should take place in the morning, i.e. ideally be started and completed between 7:00 a.m. and 11:00 a.m. Patients must adhere to the visit schedule as specified in the Flow Chart. Visits 2 (Day 2 morning) and 3 (Day 2 evening) need to be scheduled such that the trial medication could be applied according to the required dosing interval of 12 hours (± 4 hours).

6.2 DETAILS OF TRIAL PROCEDURES AT SELECTED VISITS

The study procedures which are to be performed at each visit are listed in the Flow Chart. Assessments of efficacy and safety are explained in Section 5.2 and 5.3. Assessment of POM, PA and vital signs should preferably be done by the same qualified person for a given patient throughout the study period. This person has to be adequately trained regarding POM and PA and training documentation has to be filed in the ISF.

Additional details regarding visit procedures are provided below.

6.2.1 Screening

Screening will be done during the first part of Visit 1. If a patient's eligibility is confirmed, trial treatment will be initiated. A patient's informed consent has to be obtained prior to the first trial procedures. Following the informed consent process the patient will undergo screening assessments.

It is recommended to perform study procedures in the order as listed in the Flow Chart (column "Pre"). All procedures which are necessary to assess the eligibility of a patient must be performed before randomization. A final assessment of all in- and exclusion criteria should be the last step before making the randomization call in the IRT system.

Documentation of medical history and previous therapies should be restricted to those conditions which are relevant with regard to trial indication and the assessment of the in- and exclusion criteria (see Section 3.3).

All concomitant pharmaceutical and non-pharmaceutical therapies and the corresponding baseline conditions should be documented in the CRF. Other baseline conditions should be

Trial Protocol

c03317678-02 Page 45 of 69

Proprietary confidential information © 2016 Boehringer Ingelheim International GmbH or one or more of its affiliated companies

documented if relevant with regard to trial indication and the assessment of the in- and exclusion criteria.

6.2.2 **Treatment period**

At Visit 1 (Day 1, morning), 2 (Day 2, morning), 3 (Day 2, evening), 4 (Day 3, morning) and 5 (Day 4, morning) the trial medication should be applied at the site and, if possible, by the patient himself/herself. At Visit 1, all procedures indicated in the "Pre" column of the Flow Chart should be performed before the first application of the trial medication. Procedures indicated in the "Post" column should be performed afterwards at time points as indicated.

The trial medication should be weighed, dispensed and applied after randomization without delay. The application times of trial medication will be recorded at the site in the eCRF, where application is performed at the site.

The patient should be instructed

- always to wear gloves when applying the trial medication
- to perform home assessments (warming score, mobility score, time to perceptible/ meaningful pain relieve) at time points indicated in the Flow Chart
- to refrain from using rescue medication before Visit 3 if possible. If this turns out not to be possible, another supply of rescue medication might be dispensed at visit 5
- to record intake of rescue medication (date and number of tablets) in the patient's diary
- to apply the trial medication every 12 (\pm 4) hours
- to record the time of last application of the trial medication (evening before Visit 6) in the patient's diary
- to return their patient's diary at visit 2, visit 3, visit 4, visit 5 and visit 6
- to return all unused trial and rescue medication and packaging at Visit 6

6.2.3 Follow Up Period and Trial Completion

All study procedures according to the Flow Chart should be performed.

Patients who want to discontinue the trial treatment prematurely should be asked to have Visit 6 in the morning after the last application of the trial medication and to have a Visit 7T at least 48 hours after that last application.

Patients who at the end of their trial participation still require treatment for the trial indication should be treated according to local standard of care.

Proprietary confidential information © 2016 Boehringer Ingelheim International GmbH or one or more of its affiliated companies

7. STATISTICAL METHODS AND DETERMINATION OF SAMPLE SIZE

7.1 STATISTICAL DESIGN - MODEL

This is a randomized, double-blind, placebo- and active-controlled, multi-country, multi-centre 4-arm parallel group study to investigate efficacy and tolerability of multiple doses of a topically applied combination containing diclofenac 2% + capsaicin 0.075% (2 g formulation per application; 2-times daily for 5 days (-1/+2 days) compared to placebo, as well as to diclofenac 2% and capsaicin 0.075% in patients with acute back or neck pain.

The patients will be randomised via IRT in blocks to the treatment groups diclofenac + capsaicin, diclofenac, capsaicin and placebo in a 3:3:3:1 ratio. Treatment allocation will be stratified by country and the application site (back or neck) of the study drug; the application site is classified after the POM assessments on a 0-100 mm VAS, following the 5 standard procedures, before application at Visit 1 as that site, where the worst pain is identified, and the corresponding POM is then denoted as POM_{WP}. Post-dose POM_{WP} and POM assessments for the other procedures within the corresponding stratum (back or neck) will be captured each with the same scale and the same standard procedure, respectively. For further details of POM assessments see Section 5.2.1.

Based upon these design considerations, the trial will be analysed using general linear models which will include terms for treatment, country (Germany or Russia), application site (back or neck) and the baseline POM_{WP} as continuous covariate.

7.2 NULL AND ALTERNATIVE HYPOTHESES

The primary objective of this trial is to demonstrate efficacy of the combination 2% diclofenac + 0.075% capsaicin when compared to both single components (2% diclofenac and 0.075% capsaicin) and placebo for the treatment of acute back or neck pain. This will be primarily evaluated by comparing the change in POM_{WP} between baseline (before application at Visit 1) and Visit 3 (Day 2 evening, 1 hour after application) of the combination treatment against the treatment with the single components and placebo, using two-sided tests and a 0.05 level of significance. To this purpose the following statements are hypothesised:

Null hypothesis:

There is no difference between patients treated with the combination diclofenac + capsaicin and the patients treated with diclofenac or capsaicin alone or placebo.

Alternative hypothesis:

There is a difference between patients treated with the combination diclofenac + capsaicin and the patients treated with diclofenac, patients treated with capsaicin alone and patients treated with placebo.

c03317678-02 Trial Protocol Page 47 of 69

Proprietary confidential information © 2016 Boehringer Ingelheim International GmbH or one or more of its affiliated companies

The set of hypotheses can be written as:

$$H_0$$
: $H_{0,1}$: $\mu_{diclo+caps} = \mu_{diclo}$ or $H_{0,2}$: $\mu_{diclo+caps} = \mu_{caps}$ or $H_{0,3}$: $\mu_{diclo+caps} = \mu_{placebo}$ versus

$$H_1\text{: }H_{1,1}\text{: }\mu_{diclo+caps}\neq\mu_{diclo}\text{ and }H_{1,2}\text{: }\mu_{diclo+caps}\neq\mu_{caps}\text{ and }H_{1,3}\text{: }\mu_{diclo+caps}\neq\mu_{placebo}$$

where, $\mu_{diclo+caps}$, μ_{diclo} , μ_{caps} and $\mu_{placebo}$ is the adjusted (for country and application site effect, and baseline POM_{WP}) mean change in POM_{WP} between baseline (before application at Visit 1) and Visit 3 (Day 2 evening, 1 hour after application) for patients treated with the combination diclofenac + capsaicin, diclofenac, capsaicin or placebo, respectively.

Since all partial hypotheses $H_{0,1}$, $H_{0,2}$ and $H_{0,3}$ are to be rejected in order to reject the null hypothesis H_0 , no adjustment for multiplicity issues will be made and thus all statistical testing will be performed using a two-sided, alpha = 0.05 level of significance.

The key secondary endpoints as outlined in Section 5.1.2 will be analysed hierarchically $(POM_{WP}AUC_{72} \text{ first})$ in a confirmatory way only, if statistical significance was achieved for the primary endpoint. Therefore, no alpha-adjustment for multiple endpoint testing will be applied.

All other secondary endpoints as outlined in Section 5.1.3 will be considered as supportive only.

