7.3.2 Secondary endpoint analyses

The key secondary and other secondary endpoints will be analysed with the treated set as defined for efficacy analysis in Section 7.3.

The key secondary endpoints of $POM_{WP}AUC_{72}$ and $POM_{WP}AUC_{120}$ will be analysed using an analysis of covariance (ANCOVA) including treatment, country and application site (back/neck) as fixed effects and the baseline POM_{WP} as a continuous covariate. Treatment differences will be estimated by reference to the adjusted least square means and the corresponding 95% confidence intervals. The statistical testing will be performed using a two-sided, alpha = 0.05 level of significance.

The number of patients with a decrease in POM_{WP} of at least 30% from baseline until Day 2 evening, 1 hour after drug application, will be analysed by a logistic regression model, adjusting for the categorical covariates country and application site (back/neck). The likelihood-ratio test will be used to test for differences between treatments. Adjusted odds ratios together with 95% confidence intervals will be used to quantify the effect of treatment, comparing all treatments to the treatment of diclofenac/capsaicin as the reference treatment.

The number of patients with a decrease in POM_{WP} of at least 50% from baseline until Day 2 evening, 1h after drug application, will be analysed correspondingly.

The change in POM_{WP} between baseline and the morning of Day 6 will be analysed analogously to the primary endpoint. The statistical model will be applied to the analysis of change from baseline (T0 = Visit 1 morning, before application) in POM_{WP} at times T1, T3, T4, T5 and - additionally at times T7 (=Visit 4 = Day 3 morning, 1 hour after application), T9 (= Visit 5 = Day 4 morning, 1 hour after application) and T12 (= Visit 6 = morning of Day 6).

The change in PA between baseline and Day 2 evening, before drug application (Visit 3) will be analysed analogously to the primary endpoint using all available longitudinal PA observations at the assessment times T2 = Visit 2 (Day 2 morning, before application) and T4 = Visit 3 (Day 2, evening, before application). The statistical model will be applied to the analysis of change from baseline (T0 = Visit 1 morning, before application) in PA at times T2 and T4.

The change in PA between baseline and the morning of Day 6 will be analysed analogously to the primary endpoint. The statistical model will be applied to the analysis of change from

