7.5 SECONDARY ENDPOINTS

7.5.1 Key secondary endpoints

The key secondary endpoints will be analysed using the treated set.

 $POM_{WP}AUC_{72}$ and $POM_{WP}AUC_{120}$ will be analysed using an ANCOVA model as described in the CTP. Adjusted means (with standard errors) as well as treatment contrasts will be presented together with 95% confidence intervals. The analysis will be performed using the treated set.

In addition $POM_{WP}AUC_{72}$ and $POM_{WP}AUC_{120}$ will be summarised by treatment group using descriptive statistics.

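### Do AUC72 and AUC120 lack error control because the rule that all three contrasts must win is written only for the primary endpoint?

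*Protocol*

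**What the plan says.** Protocol Section 7.2 sets out three partial null hypotheses: combination equal to diclofenac, to capsaicin, and to placebo. All three "are to be rejected in order to reject the null" hypothesis, and on that ground "no adjustment for multiplicity issues will be made". The parameters are defined as the adjusted "mean change in POM_{WP} between baseline" and Visit 3, so the formal hypotheses concern the primary endpoint alone.

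The same section then takes up the key secondary endpoints. They are tested in order, AUC72 first, "in a confirmatory way only, if statistical significance was achieved for" the primary endpoint, and for that reason "no alpha-adjustment for multiple endpoint testing will be applied".

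Protocol Section 7.3.2 gives the analysis of covariance for both AUCs and adds: "The statistical testing will be performed using a two-sided, alpha = 0.05 level of significance". SAP Section 7.5.1 says: "Adjusted means (with standard errors) as well as treatment contrasts will be presented together with 95% confidence intervals". Neither section gives the number of contrasts that must succeed, or the AUC72 result that allows AUC120 to be tested.

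**The concern.** A fixed testing order protects the 5% level only when each step is one decision made at 0.05. With three comparators, each AUC analysis yields three contrasts. The order of endpoints answers the question of several endpoints. It does not by itself answer the question of several contrasts within one endpoint.

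Read in isolation, the key secondary text could let someone claim AUC72 on one significant contrast and move on to AUC120. These endpoints are called confirmatory, so a claim of that kind would carry more than the stated 5% error. A mixed AUC72 result would also leave the success rule to be argued after unblinding.

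**Working it through.** **Inputs.** Protocol Section 7.7: 210 evaluable patients in each of the three active arms, 70 on placebo, difference 12 mm, SD 30 mm, two-sided 0.05. Three contrasts per AUC are assumed; the documents list them only for the primary endpoint (Protocol Section 7.3.1).

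**1. Reproduce the plan's own figures.** SE = 30 × √(1/n₁ + 1/n₂).

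| Contrast | SE (mm) | Smallest significant difference, 1.96 × SE (mm) | Plan | Power at 12 mm | Plan |
|---|---|---|---|---|---|
| 210 v 210 | 2.93 | 5.74 | 5.7 | 98.4% | 98% |
| 210 v 70 | 4.14 | 8.12 | 8.1 | 82.6% | 82% |

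The inputs are therefore read correctly.

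**2. Correlation of the three contrasts.** They share the combination arm.
- Diclofenac and capsaicin contrasts: (1/210) / (2/210) = 0.50.
- Either of these with the placebo contrast: (1/210) / √[(2/210)(4/210)] = 1/√8 = 0.354.

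**3. Error within one step if contrasts were claimed separately at 0.05.** Simulation of three normal statistics with these correlations, 4 million draws, primary test taken as passed.

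| Null hypotheses true | Chance of at least one false significant contrast |
|---|---|
| All three, two-sided | 13.1% |
| All three, only results favouring the combination | 6.5% (nominal 2.5%) |
| The two single-component ones, two-sided | 9.1% |
| One only, two-sided | 5% |

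For reference, three independent tests would give 1 − 0.95³ = 14.3%, and the Bonferroni bound is 15%.

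**4. Add the requirement that the primary endpoint succeeds first.** The correlation between the primary and AUC72 statistics is not in the documents, so 0 to 0.9 was used.
- True 12 mm effect on every primary contrast, none on AUC72: the primary test is passed 81% of the time. The chance of passing it and then having a false AUC72 contrast is 7.9% to 10.6%.
- No effect on the primary endpoint at all: below 0.2%.

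**5. Error if the all-three rule applies at each step.** The worst case is one true null with the other two effects very large, and the error is then that of the single remaining test: 5.0%. With all three nulls true it is 0.18%. Each step is then one decision at 0.05, which is what the fixed order requires.

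**6. Which reading does the text support?**
- The primary objective in Protocol Section 2.2 is superiority over placebo and over both components. Section 3.2 bases the design on the fixed-combination guideline.
- In Section 7.2, significance on the primary endpoint can only mean that all three partial hypotheses are rejected. Success of an endpoint therefore already has that meaning there, and the key secondary text follows directly and treats each endpoint as one step.
- No sentence in either document makes one significant contrast a confirmatory win. SAP Section 7.5.1 says only that contrasts are presented with intervals.

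**The case for a change.** The strongest case for a change is that a confirmatory rule should be written down, and that a mixed result is foreseeable. Suppose the planned standardized effect of 0.4 also held for AUC72 on every contrast. The chance that one or two contrasts, but not all three, are significant in favour of the combination is then 19%. At an assumed 0.3 it is 46%, and at 0.2 it is 58%. Some dilution is plausible: Protocol Section 3.2 times the primary assessment early so that natural recovery does not shrink the differences, whereas AUC120 runs to Day 6. Placebo has only 70 evaluable patients.

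What stands is that the rule is not repeated for the AUCs and that a mixed AUC72 result is likely enough to be worth thinking about. It does not follow that the result would be misused. Under the structure of Section 7.2, a mixed AUC72 result is a failed step and AUC120 becomes descriptive. A claim from a single contrast would need a rule that the documents do not contain. The 13% therefore measures an alternative procedure, and only in its worst case.

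**Conclusion.** No change is needed. The plan leaves unstated the success rule for AUC72 and AUC120 and the condition for moving between them. It states no rule that gives a wrong error rate. With the all-three rule carried forward from the same section, error at each step is at most 5% two-sided and no adjustment is required. If contrasts were instead claimed separately, the within-step figure would lie between 5% and 13.1% depending on which nulls are true. It would be 7.9% to 10.6% once the primary test is counted, with a real 12 mm primary effect and no AUC72 effect. For AUC120, the AUC72 step must also have been passed. The primary endpoint is untouched on either reading.

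This rests on three contrasts per AUC, normal test statistics at the planned arm sizes, and the range of correlation used in step 4. SAP Section 9 is not in the public text, so it may hold further detail.

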7.3 PLANNED ANALYSES

Three analysis datasets will be defined for the purpose of summarizing and analysing the trial data.

Treated set (TS): All randomised patients who used at least one dose of study medication will be included in the treated set. Patients having received the wrong treatment will be analysed within the planned (randomised) treatment group in the efficacy analysis and within the actual treatment group in the safety analysis.

Full analysis set (FAS): All patients included in the treated set, which provide a baseline value before application for POM_{WP} at Visit 1 and at least one POM_{WP} value during the assessment times Visit 1 (Day 1 morning, 1 hour after application), Visit 2 (Day 2, morning, 1 hour after application), Visit 3 (Day 2 evening, before application), Visit 3 (Day 2 evening, 1 hour after application), will constitute the full analysis set.

Proprietary confidential information © 2016 Boehringer Ingelheim International GmbH or one or more of its affiliated companies

7.3.1 Primary endpoint analyses

The primary endpoint 'Change in POM_{WP} between baseline (before application at Visit 1) and Visit 3 (Day 2 evening, 1 hour after application)' will be analysed utilising a restricted maximum likelihood (REML) based repeated measures approach, using all available longitudinal POM_{WP} observations at the assessment times T1 = Visit 1 (Day 1 morning, 1 hour after application), T3 = Visit 2 (Day 2, morning, 1 hour after application, T4 = Visit 3 (Day 2 evening, before application) and T5 = Visit 3 (Day 2 evening, 1 hour after application). The statistical model will be applied to the analysis of change from baseline (T0 = Visit 1 morning, before application) in POM_{WP} at times T1, T3, T4 and T5. The statistical model will include the fixed, categorical effects of treatment, country, application site (back/neck), time and treatment-by-time interaction, as well as the continuous, fixed covariates of baseline POM_{WP} and baseline-by-time interaction. The definition of baseline POM_{WP} is given in Section 7.1.

An unstructured covariance structure will be used to model the within-patient errors. In case this analysis fails to converge, other covariance structures to be employed will include Compound Symmetry, Autoregressive Model, AR (1) and Spatial Covariance, with the covariance structure converging to the best fit, as determined by Akaike's information criterion, to be used for purposes of comparing treatment effects. The Kenward-Roger approximation will be used to estimate the denominator degrees of freedom [R11-1488].

Differences between the treatment group effects (diclofenac/capsaicin - diclofenac, diclofenac/capsaicin - capsaicin, diclofenac/capsaicin - placebo) with regard to the change in POM_{WP} between T0 and T5, calculated as ' POM_{WP} at time T0 - POM_{WP} at time T5' (see Section 5.1) will be estimated by reference to the adjusted least square means and the corresponding 95% confidence intervals (CI). All statistical testing will be performed using a two-sided, alpha = 0.05 level of significance.

The primary analysis will be based on the full analysis set (FAS) as defined in Section 7.3.

In addition to the primary analysis, a separate analysis will be performed to test the heterogeneity of the strata 'application site' and 'country', respectively. In these models the two interaction terms treatment-by-stratum-by- time and stratum-by-time will be added to the primary model, respectively.

c03317678-02 Trial Protocol Page 49 of 69

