7.6 RANDOMISATION

Patients will be randomized in blocks to double-blind treatment arms diclofenac + capsaicin, diclofenac, capsaicin and placebo in a ratio 3:3:3:1. The randomization allocation will be stratified by country (Russia, Germany) and application site (back/neck). At least 40% of the randomised total population are aimed to be patients with neck/back pain, respectively. For further details on the stratified randomisation see Section 4.1.2.

BI will arrange for the randomization and the packaging and labelling of trial medication. The randomization list will be generated using a validated system, which involves a pseudorandom number generator so that the resulting treatment will be both reproducible and non-predictable. The block size will be documented in the Clinical Trial Report (CTR). Access to the codes will be controlled and documented.

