7.7 DETERMINATION OF SAMPLE SIZE

The sample size calculation is based on the assumption of superiority of the combination diclofenac + capsaicin versus diclofenac, capsaicin and placebo with regard to the primary efficacy variable 'Change in POM_{WP} between baseline (before application at Visit 1) and Visit 3 (Day 2 evening, 1 hour after application)', which reflects a pain relief on a 0-100 mm VAS about 36 h after baseline.

In a previous study investigating diclofenac in comparison to placebo in patients with acute neck pain, the true treatment difference in POM 48 h after baseline was assumed to be 12 mm [R14-1467] In another study comparing the effects of a combination of comfrey root extract with methyl nicotinate in patients with acute back pain, the standardized difference between the combination and a single ingredient was assumed to be 0.4 [R12-4427].

The sample size for this study is based on an anticipated treatment difference of 12 mm on a 0-100 mm VAS and a common standard deviation of 30 mm, yielding a standardized treatment difference of 0.4 concerning the primary endpoint. The allocation ratio to the

c03317678-02

Page 54 of 69

Proprietary confidential information © 2016 Boehringer Ingelheim International GmbH or one or more of its affiliated companies

treatment groups diclofenac + capsaicin, diclofenac, capsaicin and placebo is planned to be 3:3:3:1.

A total sample size of 700 patients (210 patients with diclofenac + capsaicin, diclofenac and capsaicin, respectively and 70 patients with placebo will have 98% power to detect a difference of 12 mm on a 0-100 mm VAS for the primary endpoint between treatment effects of diclofenac + capsaicin versus diclofenac and capsaicin, respectively (3:3 allocation ratio) and 82% power to detect the same difference between diclofenac + capsaicin and placebo (3:1 allocation ratio), assuming a common standard deviation of 30 mm and using a 0.05 two-sided significance level.

The total sample size of 700 patients will reach statistical significance with 95% confidence in the 3:3 comparisons (diclofenac + capsaicin versus diclofenac and capsaicin, respectively), when the observed treatment difference is at least 5.7 mm, and in the 3:1 comparison (diclofenac + capsaicin versus placebo), when the observed treatment difference is at least 8.1 mm.

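### The primary model gives country and application site one effect shared by all four times, so the Day 2 evening contrast may be incompletely adjusted for the randomisation strata (minor precision point)

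*Protocol*

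**What the plan says.** Randomisation (Protocol 7.6): "The randomization allocation will be stratified by country (Russia, Germany) and application site (back/neck".

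Primary model (Protocol 7.3.1): "The statistical model will include the fixed, categorical effects of treatment, country, application site (back/neck), time and treatment-by-time interaction". The model also has baseline POM_WP and its interaction with time, and an unstructured covariance. The times are T1 (1 hour after the first application), T3 (Day 2 morning, 1 hour after application), T4 (Day 2 evening, before application) and T5 (Day 2 evening, 1 hour after application). T5 is the primary time.

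Stratum-by-time terms appear only in the separate heterogeneity models, where treatment-by-stratum-by-time and "stratum-by-time will be added to the primary model, respectively".

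Protocol 7.2 defines the means under test as Visit 3 changes adjusted for country, application site and baseline. SAP 7.4.1 refers back to the protocol for the model. Its SAS code (section 9.1) is not in the supplied text.

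**The concern.** Treatment and baseline may act differently at each time, but the strata may not. A shared stratum effect is a full adjustment at T5 only if the strata differ by the same amount at T1 as about 36 hours later. The plan does not argue for this, and two of its own statements make a changing effect plausible. Section 3.2 expects topical effects after 1 to 3 days, so little change is likely at T1. Section 5.2.1 scores neck pain on procedures 1–3 and back pain on procedures 4–5, so recovery curves could differ by site.

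If the effect does change, part of the T5 stratum difference stays in the T5 residual variance. Stratified randomisation has already balanced that difference across arms, so the reported SE exceeds the true sampling error. All three contrasts must succeed, and combination versus placebo has the least planned power.

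**Working it through.** **Inputs from the documents.** Protocol 7.7: "The sample size for this study is based on an anticipated treatment difference of 12 mm on a 0-100 mm VAS"; "assuming a common standard deviation of 30 mm and using a 0.05 two-sided significance level"; 210 patients in each active arm and 70 on placebo. The 60% cap keeps each application site between 40% and 60%, so p(1−p) is 0.24 to 0.25.

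**Assumed, because the documents do not say.** A 50:50 country split, the size and time course of stratum effects, SDs at T1, T3 and T4, correlations between times, and 30 mm as the residual SD at T5.

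**Step 1: the plan's own figures.**
- Versus each component: SE = 30√(1/210 + 1/210) = 2.928; Φ(12/2.928 − 1.96) = 98.4%; smallest significant difference 1.96 × 2.928 = 5.74 mm.
- Versus placebo: SE = 30√(1/210 + 1/70) = 4.140; Φ(12/4.140 − 1.96) = 82.6%; smallest significant difference 8.12 mm.

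The stated 98%, 82%, 5.7 mm and 8.1 mm reproduce. None of them uses the strata.

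**Step 2: what a shared effect does.** Let d be the vector of true stratum differences at the four times and S the residual covariance. In large samples the common estimate is b = w′d, with w = S⁻¹1/(1′S⁻¹1). The misfit enters the fitted covariance: S* = S + p(1−p)(d−b)(d−b)′. Since w′(d−b) = 0, the weights do not change. The SE at T5 is multiplied by √(1 + p(1−p)(d₅−b)²/900).

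For one factor with 10 mm at T5 and correlation 0.5:
- Constant effect: b = 10, factor 1.0000.
- d = 2, 6, 9, 10 and equal SDs: every weight is 0.25, b = 27/4 = 6.75, factor √(1 + 0.25 × 3.25²/900) = 1.0015.
- Same d, SDs 15/24/28/30: b = 2.2, factor √(1 + 0.25 × 7.8²/900) = 1.0084.
- d = 0, 4, 9, 10, same SDs: b = 0.2, factor 1.0133.
- No stratum adjustment at all: √(1 + 0.25 × 100/900) = 1.0138.

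The same was done for AR(1) 0.8 and for an unequal pattern with correlations 0.4 to 0.9. With equal SDs and the growing effect, 57–67% of the T5 difference is removed. With T1 SDs of 10–15 it is 7–25%. With an effect absent at T1 and those SDs, almost none is removed (factors 1.012 to 1.018).

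**Step 3: both factors, combination versus placebo.** The first four rows are simulations: 700 complete patients, stratified blocks of 10, 1500 runs each. Growing means 20%, 60%, 90% and 100% of the T5 value.

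| Effects at T5 | SE, planned model | SE, by-time terms added | Excess | Power, planned → added |
|---|---|---|---|---|
| Constant over time | 4.143 | 4.146 | none | no gain |
| 5 and 5 mm, growing | 4.159 | 4.142 | 0.4% | 82.9% → 83.2% |
| 10 and 10 mm, growing | 4.208 | 4.142 | 1.6% | 81.6% → 82.5% |
| 15 and 15 mm, absent at T1 | 4.371 | 4.141 | 5.6% | 79.1% → 82.5% |
| 10 and 5 mm, near zero at T1 (formula) | 4.153–4.202 | 4.140 | 0.3–1.5% | 82.4–81.5% → 82.6% |
| 10 and 10 mm, absent at T1, T1 SD 10–15 (formula) | 4.240–4.287 | 4.140 | 2.4–3.5% | 80.8–79.9% → 82.6% |

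The last row adds two equal excess variances: √(1 + 2(1.0122² − 1)) = 1.024 and √(1 + 2(1.0179² − 1)) = 1.035. Each simulated power has a Monte Carlo SE of about √(0.82 × 0.18/1500) = 1 point, so the SEs are the firmer figures. Putting 4.371 into the formula gives Φ(12/4.371 − 1.96) = 78.4%, a loss of 4.2 points where the simulation shows 3.4. A separate simulation with 15 and 10 mm, none at T1 and a T1 SD of 15, gave a 4.0% excess and 79.6% against 82.6%.

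**Step 4: validity.** In simulation the estimates scatter equally under both models (for example 4.144 against 4.143). The type I error of the planned model was 3.9–5.2%. Only the reported SE differs.

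**Step 5: the planned power.** If 30 mm is the total SD, stratum variance included, full adjustment lowers it. With 10 mm in both factors, √(900 − 2 × 0.25 × 100) = 29.15 mm, and power versus placebo becomes 84.7%, above the plan.

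**The case against.** A reader might infer that the primary contrast is hardly adjusted for the strata, that its confidence intervals are too wide, and that the placebo comparison loses planned power. The documents support none of these as fact.

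- The first two need stratum effects that grow from near zero and an SD much smaller at T1 than at T5. The documents give no stratum effect and no SD for the earlier times. With constant effects the adjustment is complete; with equal SDs most of a growing effect is removed.
- The claim that T5 carries almost no weight in the shared estimate depends on the assumed T1 SD. With equal SDs and exchangeable correlations, T5 has weight 0.25.
- The 82% comes from a plain two-group calculation with SD 30 mm and takes no credit for stratification. The added terms may bring power above plan; their absence does not show that the plan falls short.
- The largest losses need stratum effects of about 15 mm, more than the 12 mm treatment difference.
- Both factors are in the model, as 7.1 promises, and inference stays valid. Leaving out their time interactions is a modelling choice.
- What the SAP code contains cannot be checked, because section 9.1 was not supplied.

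All of this stands, and it limits the point to an optional gain in precision. It does not remove the structural gap: the model lets baseline act separately at each time but not the randomisation strata, and a Visit 3 adjustment then rests on an unstated assumption of constant stratum effects.

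**Conclusion.** The point holds as a minor one. As written, the primary model fully adjusts the T5 contrast for country and site only if their effects are constant over T1 to T5. Otherwise the SE is conservative, with no bias and no type I inflation when strata are balanced.

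The size cannot be fixed from the documents. Under the assumptions above:
- Constant stratum effects: no loss.
- 5–10 mm effects that grow over time, or 10 mm with 5 mm near zero at T1: about 0–2% of the SE and about 1 power point versus placebo.
- 10 mm in both factors, absent at T1, with a T1 SD of 10–15: 2.4–3.5% and about 2 to 3 points.
- Effects of about 15 mm or more, near zero at T1, with a much smaller T1 SD: about 4–6% and roughly 3 to 4 points.

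These losses take 30 mm as the residual SD after strata. The sample-size statement itself is not shown to be wrong.

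**What to change.** Before unblinding, add country-by-time and application-site-by-time to the primary model in Protocol 7.3.1 and to the SAP text and code, as is already done for baseline POM_WP. Do the same in the Day 6 POM_WP model and the PA models that are analysed analogously (Protocol 7.3.2, SAP 7.5.2). The heterogeneity models can stay, with treatment-by-stratum-by-time as the added term.

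The cost is a line of text and code. The primary model gains 2 factors × (4 − 1) times = 6 fixed-effect parameters for about 700 patients; the Day 6 POM_WP model, with seven times, gains 2 × 6 = 12. If stratum effects turn out to be constant, the price is negligible: in simulation the SEs were 4.143 and 4.146, less than 0.1% apart.
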